Appendix 2 Concomitant medication

Allowed drugs:

- Furosemide
- Ursodeoxycholic acid
- Taurine
- Shousaikoto
- LAC-B (Bifidobacterium)
- Omeprazole
- Monoammonium glycyrrhizinate, glycine, L-cysteine hydrochloride hydrate
- Monoammonium glycyrrhizinate, glycine, DL-methionine
- Azosemide
- Spironolactone
- Tolvaptan
- Glutathione
- Flavin Adenine Dinucleotide Sodium
- Rebamipide
- Teprenone
- Polaprezinc
- Sodium Alginate
- Famotidine
- Lafutidine
- Rabeprazole
- Esomeprazole
- Lansoprazole
- Vonoprazan
- Mosapride
- L-Isoleucine, L-leucine, L-valine
- L-isoleucine, L-leucine, L-lysine hydrochloride, L-threonine, L-valine, L-arginine hydrochloride, L-histidine monohydrochloride, L-tryptophan, gelatin, rice bran oil, dextrin, retinol palmitate, ergocalciferol, bisbentiamine, riboflavin, pyridoxine hydrochloride, cyanocobalamin, folic acid, sodium ascorbate, tocopherol acetate, phytonadione, calcium pantothenate, nicotinamide, biotin, choline bitartrate, magnesium sulfate hydrate, calcium glycerophosphate, potassium phosphate, sodium ferrous citrate, cupric sulfate, zinc sulfate hydrate, potassium iodide, manganese sulfate, potassium chloride, manganese sulfate
- L-isoleucine, L-leucine, L-lysine, L-methionine, L-phenylalanine, L-threonine, L-tryptophan, L-valine, L-alanine, L-arginine, L-aspartic acid, L-histidine, L-proline, glycine
- Amlodipine
- Candesartan cilexetil
- Telmisartan
- Atenolol
- Benidipine
- Valsartan
- Irbesartan
- Cilnidipine
- Azilsartan
- Nifedipine
- Insulin

- Sitagliptin
- Alogliptin
- Metformin
- Lamivudine
- Adefovir pivoxil
- Daclatasvir
- Asunaprevir
- Ledipasvir, sofosbuvir
- Lactulose
- Rifaximin
- Magnesium Oxide
- Sodium picosulfate hydrate
- Sennoside A, B
- Pravastatin
- Rosuvastatin
- Atorvastatin
- Ezetimibe
- Allopurinol
- Flunitrazepam
- Etizolam
- Brotizolam
- Zolpidem
- Lactomin, clostridium butyricum, bacillus mesentericus
- Febuxostat
- Aspirin (acetylsalicylic acid)
- Edoxaban
- Loratadine
- Fexofenadine hydrochloride
- Pancreatic digestive enzymes, aspergillus producing digestive enzymes, bacterial lipase, berizym
- Menatetrenone
- Loxoprofen sodium hydrate
- Levodopa
- Carbidopa hydrate
- Benserazide hydrochloride
- Pregabalin
- L-carbocisteine
- Tramadol hydrochloride
- Glucose
- Thiamine disulfide, pyridoxine hydrochloride, hydroxocobalamin acetate
- Purified sodium hyaluronate
- Pirenoxine
- Cyanocobalamin
- Pranoprofen
- Brinzolamide, timolol maleate
- Prednisolone
- Levothyroxine sodium hydrate
- Eldecalcitol
- Chlordiazepoxide
- Methocarbamol

- Sodium gualenate hydrate
- Heparinoid
- Pantoprazole

Not permitted during hospitalisation:

- Verapamil
- Zanthoxylum fruit, ginseng, processed ginger, koi
- Cefazolin sodium
- Cefotiam hydrochloride
- Piperacillin sodium
- Mefenamic acid
- Acetaminophen
- Ibuprofen
- Diclofenac sodium
- Shakuyakukanzoto (glycyrrhizic acid, paeoniflorin)
- Adenosine triphosphate disodium hydrate

Not permitted within 14 days before Screening and from 14 days before Day -1 (check-in) to Day 3 (discharge):

- Albumin preparation

Other concomitant medication will be discussed with the Sponsor.

## ABBREVIATIONS

Abbreviations	Definitions
AE	adverse event
ALT	alanine transaminase
ALP	alkaline phosphatase
ANCOVA	analysis of covariance
AST	aspartate transaminase
ATC	anatomical therapeutic chemical
BDR	blinded data review
BLQ	below limit of quantification
BMI	body mass index
CI	confidence interval
CV	coefficient of variation
DP	decimal places
DMC	data monitoring committee
ECG	electrocardiogram
FAS	full analysis set
ITT	intent-to-treat
LLOQ	lower limit of quantitation
MedDRA	medical dictionary for regulatory activities
MMRM	mixed model repeated measures
PD	pharmacodynamics
PDPOP	PD Population
PK	pharmacokinetics
PKPOP	PK Population
PP	per protocol
PT	preferred term
RAND	all subjects randomized population
SAP	statistical analysis plan
SAE	serious adverse event
SAF	safety population
SD	standard deviation
SOC	system organ class
TEAE	treatment emergent adverse event
TESAE	treatment emergent serious adverse events
ULN	upper limit of normal range
WHO	World Health Organization

## LIST OF PK AND/OR PD PARAMETERS

List of PK Parameters		
Parameters	Unit	Definitions
AUC 0-last	h•ng/mL	Area under the plasma concentration-time curve from zero up to the last quantifiable concentration time point
AUC 0-∞	h•ng/mL	Area under the plasma concentration-time curve from zero up to infinity with extrapolation of the terminal phase
AUC 0-∞	h•ng/mL	Unbound area under the concentration-time curve from time zero to infinity with extrapolation of the terminal phase
AUC% ex	%	Area under the plasma concentration-time curve extrapolated from the last quantifiable concentration time point to infinity in % of the total AUC 0-∞
C max	ng/mL	Maximum plasma concentration after administration
C last	ng/mL	Last quantifiable concentration
CL	L/h	Total clearance
CLu	L/h	Unbound total clearance
λ z	/h	Elimination rate constant from the central compartment
Lower limited of λ z	h	Lower data point used for the estimation of λ z
MRT	h	Mean residence time
Number of λ z points	-	Number of data point used for the estimation of λ z
t 1/2	h	Terminal elimination half-life in plasma concentration-time course
t max	h	Time of maximum plasma concentration after administration
Upper limited of λ z	h	Upper data point used for the estimation of λ z
V ss	L	Volume of distribution at steady state
V z	L	Volume of distribution during terminal phase

## 1. INTRODUCTION

This statistical analysis plan (SAP) is based on the final protocol (v3.0) dated 06-FEB-2019. The plan covers statistical analysis, tabulations and listings of the study data to investigate the pharmacokinetics of MCI-186 in subjects with severe hepatic impairment compared to subjects with normal hepatic function.

Any statistical analysis details described in this document supersede any description of statistical analysis in the protocol.

## 2. STUDY OBJECTIVE AND ENDPOINTS

### 2.1. Study Objectives

#### 2.1.1. Primary Objective

The primary objective of this study is to assess the PK of MCI-186 after a single IV infusion of 30 mg/hour in subjects with severe hepatic impairment compared to subjects with normal hepatic function.

#### 2.1.2. Secondary Objective

The secondary objective of this study is to investigate the safety and tolerability of MCI-186 in subjects with severe hepatic impairment and in subjects with normal hepatic function.

### 2.2. Study Endpoints

#### 2.2.1. Primary Endpoints

The following primary PK parameters of MCI-186 will be calculated in the study:

- $C_{max}$
- Area under the concentration-time curve from time zero to the last quantifiable concentration ( $AUC_{0-last}$ )
- $AUC_{0-\infty}$

#### 2.2.2. Secondary Endpoints

The following secondary endpoints will be evaluated during the study:

#### Pharmacokinetic parameters of MCI-186:

- $t_{1/2}$
- Time to reach peak concentration ( $t_{max}$ )
- Terminal elimination rate constant ( $\lambda_z$ )
- Total clearance (CL)
- Volume of distribution at steady state ( $V_{ss}$ )
- Volume of distribution during the terminal phase ( $V_z$ )

- Mean residence time (MRT)
- Unbound area under the concentration-time curve from time zero to infinity (AUC0-∞)
- Unbound total clearance (CLu)

Pharmacokinetic parameters of the sulfate conjugate:

- Cmax
- AUC0-last
- AUC0-∞
- t1/2
- tmax

Safety and Tolerability

- Incidence of adverse events (AEs) and serious adverse events (SAEs)
- Physical examination
- Vital signs (blood pressure, pulse rate and body temperature)
- 12-lead electrocardiogram (ECG) parameters
- Laboratory assessments including biochemistry, haematology, coagulation and urinalysis
- Columbia-Suicide Severity Rating Scale (C-SSRS; see Appendix 1 in Section 14 of the Protocol)

### 3. STUDY DESIGN

#### 3.1. Study Design

This is a Phase I, open-label, single-dose study to evaluate the pharmacokinetics of MCI-186 in male and female subjects with severe hepatic impairment (Group 1, n = 6), defined using the Child-Pugh classification, and in male and female subjects with normal hepatic function (Group 2, n = 6). Subjects may be replaced or additional subjects may be enrolled to ensure a minimum threshold of 6 completing subjects per group.

- Group 1: Subjects with severe hepatic impairment (Child-Pugh total score of 10 to 14 [Grade C])
- Group 2: Healthy subjects with normal hepatic function to match Group 1 for age, body weight and gender

All subjects will be administered 30 mg MCI-186 over 60 minutes on the morning of Day 1. An infusion time window of ±3 minutes is permitted.

#### Order of subject enrolment

Individual matching of healthy subjects will be performed for the subjects with hepatic impairment. Therefore, after the end of study assessments are completed in subjects with hepatic impairment, healthy subjects will be enrolled. Each healthy subject will be individually

matched with a hepatic impairment subject with respect to age ( $\pm 15$  years), body weight ( $\pm 20\%$ ) and gender. Matched healthy subjects may be recruited by any study site, not necessarily by the same site which recruited the subject with hepatic impairment.

If there are significant safety concerns, the study may be stopped as described in Section 4.5 of the Protocol.

#### Study periods and duration of study

The study consists of:

- A pre-admission Screening period (Day -21 to Day -2)
- A treatment hospitalisation period (Day -1 to Day 3) with single IV infusion of 30 mg MCI-186 over 60 minutes (including an infusion time window of  $\pm 3$  minutes) on Day 1, and PK blood sampling until 48 hours post-dose.  
All subjects will be confined to the study centre from Day -1 to Day 3. Safety assessments will be performed until discharge.
- A Follow-up Period (Day 7 + 2 days). An end of study assessment will be performed.

The duration of participation for each individual subject is expected to be up to 30 days.

#### **3.2. Schedule of Study Procedures**

Study assessments are summarised in the time and events schedule (Table 1).

**Table 1 Time and events schedule**

Study Period	Screening			Treatment Hospitalisation			Follow-up		
	-21 to -2	-1	1	2	3	7 (+2)			
Time point									
Informed consent	X								
Confinement									
Outpatient	X								
Inclusion/exclusion criteria	X	X	X						
Demography & medical history	X								
Physical examination	X	X	X 				X 	X	X 
Weight	X	X					X	X	X
Height	X								
BMI	X	X							
Vital signs	X	X	X				X	X	X
12-lead ECG	X	X	X				X	X	X
Urine drugs of abuse & breath alcohol test	X	X							
Biochemistry, haematology, coagulation & urinalysis	X	X					X	X	X
C-SSRS		X					X		

Study Period	Screening		Treatment Hospitalisation						Follow-up		
	Study Day	-21 to -2	-1	1			2			3	7 (+2)
Time point											
Hepatic impairment assessment (Child-Pugh classification; Group 1 only)				■	■	■	■	■	■	■	■
eGFR	X	X								X	X
Hepatitis B & C and HIV	X	X								X	X
Pregnancy test in females	X	X								X	
Protein binding blood sampling		X									
IMP administration				←		→					
PK sampling (blood) 			■	■	■	■	■	■			
AE and concomitant medications			←								↑

Abbreviations: AE=adverse event; BMI=body mass index; C-SSRS=Columbia-Suicide Severity Rating Scale; ECG=electrocardiogram; eGFR=estimated glomerular filtration rate; HIV=human immunodeficiency virus; IMP=Investigational Medicinal Product; PK=pharmacokinetic.

- IMP administration starting time. IMP will be administered over 60 minutes. The permitted infusion time window is  $\pm 3$  minutes
- Abbreviated physical examination only
- The time windows for PK sampling during the study are as follows. All times relate to the infusion start time:
  - pre-dose: -60 to -30 minutes
  - $\pm 5$  minutes
  - +3 minutes from end of infusion
  - $\pm 5$  minutes

- [REDACTED] ±15 minutes

### **3.3. Sample Size and Power Considerations**

The planned sample size of 6 evaluable subjects with severe hepatic impairment and 6 evaluable healthy subjects is not based on a power calculation, but is based on the FDA recommendation for at least 6 evaluable subjects per group.

In total, 12 subjects will be enrolled to ensure 6 subjects per group complete the study.

## **4. PLANNED ANALYSIS**

### **4.1. Interim Analysis**

No interim analysis is planned for this study.

### **4.2. Final Analysis**

This SAP will be finalized before database lock. Final data analysis will be conducted after database lock.

## **5. ANALYSIS POPULATIONS**

Analysis Population	Definition
Safety analysis set (SAF)	All subjects who receive at least one dose of IMP
PK analysis set (PKPOP)	All subjects, who have received at least one dose of IMP and for whom the PK data are considered sufficient and interpretable.

PK=pharmacokinetic

The SAF or All subjects will be used for study population-related evaluations. The SAF will be used for all safety evaluations. The PKPOP will be used for the PK analyses.

## **6. STATISTICAL CONSIDERATIONS**

### **6.1. Descriptive Statistics**

#### **(1) Non-PK related**

Continuous data will be summarized descriptively using the number of subjects in the analysis set (N), the number of observations (n), mean, standard deviation (SD), median, minimum and maximum. Categorical data will be summarized using frequency counts and percentages. The denominator for the percentages will be the total number of subjects in the treatment group and analysis population being presented, unless otherwise specified.

**(2) PK related**

Plasma concentrations will be summarized descriptively using N, n, arithmetic mean, SD, CV%, minimum, median, maximum, geometric mean and geometric CV%.

The plasma and urine PK parameters will be summarized descriptively using N, n, arithmetic mean, SD, median, minimum, maximum, CV%, geometric mean and geometric CV%  
CV% and Geometric CV% will be calculated as follows:

$$CV\% = \frac{\text{standard deviation}}{\text{arithmetic mean}} \times 100$$

$$\text{Geometric CV\%} = \sqrt{[\exp(\sigma^2) - 1]} \times 100$$

where  $\sigma$  represents the standard deviation computed on the natural logarithmic transformed concentrations.

**6.2. Statistical Tests**

Unless otherwise specified, The significance level of the statistical test will be 5% (two-sided). The two-sided confidence level of the confidence interval will be 95%. The two-sided confidence level for comparison between groups will be 90%.

**7. DATA CONVENTIONS**

**7.1. Analysis Variable Definitions**

**7.1.1. Study Subjects**

**7.1.1.1. Protocol Deviations**

Protocol deviations will be identified and documented during a data review prior to database lock and confirmed by database lock. Important protocol deviations will be defined as important deviations that may significantly impact the completeness, integrity, accuracy, and/or reliability of the study data and may significantly affect a subjects rights, safety, or well-being.

**7.1.1.2. Demographic and Other Baseline Characteristics**

**(1) BMI**

BMI will be recalculated using the formula below and reported to 1dp.

$$\text{BMI (kg/m}^2\text{)} = \text{weight at screening (kg)} / \{\text{height at screening (m)}\}^2$$

**(2) Child-Pugh Classification**

The maximum score a subject can get from the classification will be 14 and not 15. This is because subjects with severe encephalopathy will be excluded from the trial (exclusion criteria

19), so the maximum score a subjects can get from the ‘Hepatic Encephalopathy’ question is 2 and not 3, hence the maximum score obtainable will be 14 and not 15.

#### **7.1.1.3. Medical History**

Medical history will be coded according to the Medical Dictionary for Regulatory Activities (MedDRA) version 21.1 or later.

#### **7.1.1.4. Prior or Concomitant Medication**

Medications will be coded according to the World Health Organisation Drug Dictionary (WHO-DD) SEP 2018 version.

##### **(1) Prior Medication**

Prior medication is any medication that was stopped prior to administration of IMP.

##### **(2) Concomitant Medication**

Concomitant medication is any medication that is ongoing at the time of dosing or started after administration of IMP, including prescription and over the counter medications.

### **7.1.2. Safety Assessments**

#### **7.1.2.1. Adverse Events**

Adverse events will be coded according to the MedDRA version 21.1 or later.

An AE is any untoward medical occurrence in a patient or clinical investigation subject administered a pharmaceutical product that does not necessarily have a causal relationship with this treatment.

An SAE is defined as any untoward medical occurrence that at any dose:

- Results in death
- Is life-threatening
- Requires hospitalisation or prolongation of existing hospitalisation
- Results in persistent or significant disability or incapacity
- Is a congenital anomaly or birth defect
- Is an important medical events

##### **(1) Treatment Emergent Adverse Events/ Treatment Emergent Serious Adverse Events (TEAEs/TEsAEs)**

AEs/SAEs will be classified as ‘treatment-emergent’ if they arise following the first administration of IMP or if a pre-dose AE increases in severity following dosing.

##### **(2) Adverse Drug Reaction**

A TEAE is considered an “adverse drug reaction” if it has been assessed as having a “reasonable possibility” in relationship to the study drug.

##### **(3) Duration of Adverse Events**

Duration of Adverse Events (days) = AE stop date – AE start date + 1

### 7.1.2.2. 12-Lead ECG

#### (1) Criteria for pre-defined limit

12-lead ECG:

- QTcF :  $\leq 450$  msec,  $450 < QTcF \leq 480$  msec,  $480 < QTcF \leq 500$  msec,  $> 500$  msec
- Change from baseline in QTcF :  $> 30$  msec,  $> 60$  msec

### 7.1.3. Pharmacokinetics Evaluation

#### 7.1.3.1. Plasma Concentration

For the calculation of the summary statistics, concentration values reported as below the limit of quantification (BLQ) will be set to 0. For the calculation of the geometric mean and geometric CV%, concentration values reported as BLQ will be set to  $\frac{1}{2}$  of LLOQ. LLOQ for sulfate is not defined because sulfate conjugates are determined as Unchanged MCI-186 after hydrolysis. However “253.25 / 174.20” will be expediently used as LLOQ of sulfate only to calculate the geometric mean and geometric CV%.

#### 7.1.3.2. Pharmacokinetic Parameters

##### (1) Below the limit of quantification

For the calculation of PK parameters, actual sampling time (in hours rounded to 2 decimal places) relative to dosing should be used. Concentration below the limit of quantification (BLQ) will be imputed with a value of 0. For calculation of AUCs, missing data will be treated as if the respective sample never had been scheduled for the calculation by the linear-linear trapezoidal rule.

## 7.2. Analysis Visit Definitions

#### (1) Non-PK related

The date of the first dose of study drug is defined as Day 1.

Unless otherwise specified, baseline will be the last observed value of the parameter of interest prior to the first intake of study drug on Day 1 (this includes unscheduled visits). For other visits, if there are multiple data in a window, the closest data to nominal day will be used. If the distance to the nominal day is the same, the data of later date will be used.

#### (2) PK related

The allowable time window will be the following.

Pre-dose	Within 30 to 60 minutes before dosing
[REDACTED]	Scheduled time $\pm 5$ minutes
[REDACTED]	Within 3 minutes after dosing

[REDACTED]	Scheduled time ± 5 minutes
[REDACTED]	Scheduled time ± 15 minutes

### 7.3. Data Handling Convention for Missing Data

#### (1) Non-PK related

Adverse events:

If severity or relationship is found to be missing the most severe occurrence will be imputed for the summary of interest.

For AE start missing or partial dates, the AE will be treated as TEAE if it cannot be determined to be a non-TEAE.

Other Safety-related endpoints:

For other safety-related summaries, only observed data will be used. Unless otherwise specified, missing safety data will not be imputed.

#### (2) PK related

For PK summaries, only observed data will be used. Missing PK data will not be imputed.

## 8. STATISTICAL METHODOLOGY

### 8.1. Study Subjects

#### 8.1.1. Subject Disposition

Subject disposition will be summarized on the SAF (*Table 14.1.1*).

Subject disposition will be listed on the SAF (*Listing 16.2.1*). Inclusion and exclusion criteria deviation at screening will be listed on All Subjects (*Listing 16.2.2.1*).

#### 8.1.2. Analysis Populations

Analysis populations will be summarized (*Table 14.1.2*).

Analysis populations will be listed on the SAF (*Listing 16.2.3*).

#### 8.1.3. Protocol Deviations

Important Protocol Deviations will be listed on the SAF (*Listing 16.2.2.2*).

#### 8.1.4. Demographic and Other Baseline Characteristics

The following demographic and other baseline characteristics will be used.

	Category	Descriptive
Sex	Male, Female	
Age (years)	18 – 65 > 65	Yes
Height (cm)		Yes

Weight (kg)		Yes
BMI (kg/m^2)		Yes
Race	American Indian or Alaska Native, Asian, Black, Native Hawaiian or Other Pacific Islander, White, Multiple, Other	
Ethnicity	Not Hispanic or Latino, Hispanic or Latino, Unknown	
eGFR on Day -1		Yes
Child-Pugh Score on Day -1		Yes
Alcohol Consumption	Never drank, Former drinker, Current drinker	

Demographic and other baseline characteristics will be summarized on the SAF (*Table 14.1.3*). Demographic data will be listed on the SAF (*Listing 16.2.4.1*) and other baseline characteristics (including alcohol consumption) will be listed on the SAF (*Listing 16.2.4.2*). Child-Pugh classification data will be listed on the SAF (*Listing 16.2.4.3*) for hepatically impaired subjects only.

### **8.1.5. Medical History**

Medical history data will be listed on the SAF (*Listing 16.2.4.4*). Other Screening and Day -1 assessments (alcohol breath test) will be listed on the SAF (*Listing 16.2.4.5*).

### **8.1.6. Prior or Concomitant Medications**

Prior medication and concomitant medication will be summarized separately on the SAF (*Table 14.1.4 and Table 14.1.5*).

Prior and concomitant medication will be listed on the SAF (*Listing 16.2.5.1*).

### **8.1.7. Study Drug Administration**

Study drug administration will be listed on the SAF (*Listing 16.2.5.2*).

## **8.2. Safety Assessments**

Safety assessments will be made on the SAF population.

### **8.2.1. Adverse Events**

Overall summary including the following will be presented (*Table 14.3.1.1*).

- Subjects with at least one AE
- Subjects with at least one SAE
- Subjects with at least one TEAE
- Subjects with at least one TESAE
- Subjects with at least one adverse drug reaction
- Subjects with at least one serious adverse drug reaction

- Subjects with at least one TEAE leading to discontinuation of study drug
- Subjects with at least one TESAE leading to discontinuation of study drug
- Subjects with at least one adverse drug reaction leading to discontinuation of study drug
- Subjects with at least one serious adverse drug reaction leading to discontinuation of study drug

The following summaries also will be conducted.

- TEAEs by SOC and PT (*Table 14.3.1.2*)
- TESAEs by SOC and PT (*Table 14.3.1.3*)
- Adverse drug reactions by SOC and PT (*Table 14.3.1.4*)
- TEAEs by SOC, PT and severity (*Table 14.3.1.5*)
- TEAEs by SOC, PT and relationship to study drug (*Table 14.3.1.6*)

Each of the summaries will be done at the subject level - multiple occurrences of the same event within a subject will be counted once in the summaries by SOC and PT; multiple occurrences of the same event within a subject will be counted once in the maximum severity category (severe > moderate > mild) and/or maximum drug relationship category (reasonable possibility/no reasonable possibility) and/or the earliest duration. If intensity or relationship is found to be missing, the most severe occurrence will be imputed for that particular summary. These summaries will also present the number of events that occurred, and multiple occurrences of the same event within a subject will all be accounted for in the maximum intensity category and maximum relationship category they were classed as.

The following will be listed.

- All AEs (*Listing 16.2.7*)
- Death (only if any deaths occur)

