4.5 Withdrawal of individual subjects

A subject will be withdrawn if ANY of the following criteria are met:

- The subject wishes to withdraw from further participation
- The subject is significantly noncompliant with the Protocol
- The subject becomes pregnant
- Continuing in the study would be detrimental to the subject's safety in the opinion of the Investigator, e.g.,
 - The subject experiences intolerable AEs or SAEs
 - The subject has clinically significant changes in safety parameters at any of the post-dose time points, as confirmed with a repeat assessment performed as soon as possible after the initial out-of-range result

In addition, a subject may be withdrawn at any time for reason(s) other than those listed here.

If a subject is discontinued prematurely from the study, the date the subject is withdrawn from the study and the reason for withdrawal will be recorded on the electronic case report form (eCRF).

In case of withdrawal of a subject, the Follow-up assessments should be performed, as far as possible (Section 5.2.3).

Any withdrawal due to an AE or for any safety reason should be assessed for seriousness according to Section 8.2.

Any unresolved AE or SAE will be followed up according to Section 8.9.

In the event that a subject elects not to return to the clinic for the end of study visit, the Investigator must make every effort to contact the subject to review all AEs. In the event that a subject drops out of the study at any time, the reason for discontinuation must be fully documented in the source documents and the eCRF. The study centre personnel will document the AEs and any other assessments in the source documents and will make every effort to complete all required end of study assessments.

Subjects withdrawn for non-treatment-related reasons may be replaced at the discretion of the Sponsor and Investigator. Replacement subjects will receive the treatments intended for the withdrawn subject.

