10.3.5.3 Adverse events

Adverse events will be coded using MedDRA (version 20.0 or later). A by-subject AE data listing including start/stop times, verbatim term, Preferred Term, System Organ Class (SOC), severity, seriousness, relationship to treatment and outcome will be provided. All AEs that start before dosing will be classified as baseline AEs and will be listed only. All treatment-emergent AEs (TEAEs), i.e., AEs which start on or after dosing, will be tabulated. In the tabulations, numbers of subjects with TEAEs and numbers (occurrences) of TEAEs will be counted separately.

The following summaries of TEAEs will be presented:

- Summary of TEAEs by SOC and Preferred Term
- Summary of TEAEs by SOC, Preferred Term and severity of event
- Summary of TEAEs by SOC, Preferred Term and relationship to treatment

The above TEAE summaries will be produced by time interval as appropriate.

In addition, details of AEs and SAEs leading to withdrawals will be listed separately.

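### The SAP's event counts, read literally, put every repeat of an adverse event in the subject's worst severity and relationship category; the protocol's separate listing of events leading to withdrawal is also missing

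*SAP*

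**What the plan says.** **Counting rule.** SAP 8.2.1 first sets a subject-level rule: a subject with repeats of the same event is counted once, in the highest severity and the strongest relationship category. It then adds event counts: "These summaries will also present the number of events that occurred". For these it states that "multiple occurrences of the same event within a subject will all be accounted for in the maximum intensity category and maximum relationship category", and the sentence closes with a short clause saying that these are the categories in which the events were classed. The affected tables are 14.3.1.5 (severity) and 14.3.1.6 (relationship).

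Protocol 10.3.5.3 is briefer: "In the tabulations, numbers of subjects with TEAEs and numbers (occurrences) of TEAEs will be counted separately". It does not say in which severity or relationship category a repeat occurrence belongs.

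**Withdrawals.** The overall summary, Table 14.3.1.1, has four discontinuation rows (TEAEs, serious TEAEs, adverse drug reactions and serious adverse drug reactions). All are tied to study drug; the first reads "Subjects with at least one TEAE leading to discontinuation of study drug". The AE listings named in SAP 8.2.1 are Listing 16.2.7 (all AEs) and a listing of deaths if any occur.

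Protocol 10.3.5.3 also promises that "details of AEs and SAEs leading to withdrawals will be listed separately". Protocol 4.5 allows withdrawal for intolerable AEs, or on safety grounds such as "The subject has clinically significant changes in safety parameters at any of the post-dose time points", once confirmed by a repeat assessment. SAP section 1 gives the SAP precedence on the analysis details it describes, and SAP section 10 declares no changes from the protocol.

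**The concern.** A worst-category rule suits a count of subjects, because each subject can occupy only one category. An event count has a different purpose: it should show how many events of each severity and relationship were recorded. Carrying the subject-level maximum over to it moves milder or unrelated repeats into the severe or related cells, and the event column no longer describes the occurrences.

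Safety and tolerability in severe hepatic impairment is the secondary objective, and each group has about 6 subjects. One subject with several repeats can therefore visibly change the severity profile of a group.

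The withdrawal gap concerns traceability. The drug is a single infusion, so the discontinuation rows cannot show a subject withdrawn for an AE after the infusion has ended. The output that the protocol planned for such subjects is not itemised in the SAP. One such withdrawal would be 1 of 6, or 17%, of a group.

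**Working it through.** The plan gives no figure to reproduce. The check applies the SAP rule literally to hypothetical event patterns and compares it with counting each occurrence as recorded.

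**Inputs.** The counting rules come from SAP 8.2.1. Severity and relationship are recorded for every AE (Protocol 8.6). I take *same event* to mean the same preferred term. The event patterns are illustrations; the documents do not predict them.

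**Formulas.** Let one subject have *n* occurrences of one preferred term, of which *m* were recorded at that subject's maximum category.

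- As recorded, the maximum category receives *m* events.
- Under the SAP rule, it receives all *n*.
- The excess is *n − m*, which is zero when all repeats share one category.

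| Occurrences in one subject | Total events | Severe / related, SAP rule | Severe / related, as recorded |
|---|---|---|---|
| 2 mild unrelated, 1 severe related | 3 | 3 / 3 | 1 / 1 |
| 1 mild unrelated, 1 severe related | 2 | 2 / 2 | 1 / 1 |
| 3 mild unrelated, 1 moderate unrelated, 1 severe related | 5 | 5 / 5 | 1 / 1 |
| 2 mild unrelated | 2 | 0 / 0 | 0 / 0 |
| 2 severe related | 2 | 2 / 2 | 2 / 2 |

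In the first row *n* = 3 and *m* = 1, so the excess is 3 − 1 = 2. Mild events fall from 2 to 0. In every row the total number of events is the same under both rules and the subject is counted once.

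**Study-drug rows.** The infusion lasts 60 minutes with a 3-minute window either way, so drug can be stopped for at most 63 minutes, or 1.05 h. From dosing on Day 1 to Follow-up on Day 7 to Day 9 is 6 to 8 days, or 144 to 192 h.

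- 1.05 / 144 = 0.73%
- 1.05 / 192 = 0.55%

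The four discontinuation rows can thus draw on about 0.5% to 0.7% of the post-dose period. This is a share of clock time. It does not estimate the share of events or withdrawals missed, because AE risk need not be even over the period.

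**Listings side by side.** The protocol plans a by-subject AE listing and a separate listing of events leading to withdrawal. SAP 8.2.1 names the first and a death listing, but not the second. The omission is not declared in SAP section 10.

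**The case against.** The strongest reply has four parts.

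1. **The sentence can be read another way.** Its closing clause could mean that each event goes into the category it was itself given. That reading is possible, but the words that all occurrences go into the maximum category point the other way. Two programmers could produce different tables from it, so rewording is needed under either reading.

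2. **The protocol is not contradicted on counting.** A reader might infer that the SAP rule breaches Protocol 10.3.5.3. It does not: subjects and occurrences are still counted separately, and the protocol is silent on the category of repeats. The fault lies in the rule itself.

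3. **The effect is conditional and errs towards caution.** It needs repeats of one event in one subject with differing categories, after a single dose and 6 to 8 days of follow-up. It can overstate severity but not hide it. It applies to both groups, no formal safety analysis is planned (Protocol 10.3.5.2), and the protocol's by-subject listing shows each event's severity and relationship. The stopping criterion in Protocol 4.6 acts on an individual event, not on these tables. All of this stands and keeps the point small.

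4. **Withdrawals are not invisible.** A reader might infer that only AEs stopping the study drug are tabulated, or that AEs behind later withdrawals go unreported. The documents do not support this. SAP 8.2.1 tabulates all TEAEs, serious TEAEs and adverse drug reactions by system organ class and preferred term, and TEAEs also by severity and relationship. Listing 16.2.7 covers all AEs. SAP 8.1.1 summarises and lists disposition, though without saying whether withdrawal reasons are shown. The protocol promised a listing of these events, not a table. It can also be argued that the SAP's silence leaves the protocol's listing in force. That is arguable, but a SAP that itemises its AE listings and declares no change should name it.

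**Conclusion.** The point holds as a minor one.

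On its natural reading, the SAP's event-count rule overstates severe and related event counts in Tables 14.3.1.5 and 14.3.1.6 whenever repeats of one event in one subject differ in category. The illustration gives 3 instead of 1. This rests on the literal reading of the sentence and on such repeats occurring; the documents do not show how likely they are. It would therefore be too strong to say that the counts will be inflated. Subject-level incidence and total event counts are correct under either rule.

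The secondary point also holds: the discontinuation rows cannot show an AE withdrawal after the infusion, and one listing planned in the protocol is missing without being declared. The underlying events remain in the TEAE tables and in Listing 16.2.7, so what is lost is ready identification, not the data.

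Neither point affects the primary PK analysis.

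**What to change.** - **SAP 8.2.1, counting rule.** Limit the maximum-category rule to subject counts. Replace the event-count sentence with wording such as: *Event counts include every occurrence, each in the severity and relationship category recorded for that occurrence.*
- **SAP 8.2.1, listings.** Add the separate listing of AEs and SAEs leading to withdrawal from the study, or record and justify its omission in SAP section 10.
- **Table 14.3.1.1, optional.** Add a row for subjects with at least one TEAE leading to withdrawal from the study, beside the existing study-drug rows.

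The cost is a few lines of SAP text, a small programming change and one short listing. No new data are needed: severity and relationship are on the AE form (Protocol 8.6) and the reason for withdrawal is on the eCRF (Protocol 4.5). If that reason does not name the event, the link can be made at the data review before database lock, which is manageable with about 12 subjects.
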